12.7 Safety Analyses

All safety analyses will be presented using the Safety analysis set.

12.7.1 Primary Endpoints

The primary endpoints are:

- Safety and reactogenicity of the vaccine(s): incidence of AEs, SAEs, \geq Grade 3 study vaccine-related AEs within 4 weeks of vaccination
- Safety of the vaccines with nivolumab: incidence of AEs, SAEs, \geq Grade 3 AEs within 4 weeks of dosing
- Incidence of AESI
- Number and proportion of participants reporting TEAEs within each treatment group
- Number and proportion of participants within each treatment group with potentially clinically significant laboratory values and vital signs within each treatment group
- Change from baseline in laboratory tests and vital sign measurements to each time point of collection

12.7.1.1 Adverse Events

The number and percentage of participants reporting each adverse event, including the number of events, will be summarised by SOC and PT coded according to the MedDRA dictionary. Participants are only counted once within each SOC and PT. AEs will be sorted by decreasing frequency within each SOC and PT according to the overall treatment group.

In addition, summaries will be provided for the subset of AEs, SAEs, and Grade 3 or greater AEs that occurred within 28 days of first vaccination and second vaccination (vaccination day + 27 days) separately.

AESI will also be tabulated by PT for all events occurring during the study.

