#### *8.2.4 Recording and Assessment of Adverse Events by the Investigator*

Solicited adverse events are recorded in the eDiary up to 7 days post-vaccination. All other adverse events are recorded in the eCRF at all clinic visits throughout the study. All adverse events, both those observed by study team members and those spontaneously reported by the participant, will be recorded in the eCRF. Solicited adverse events will be reported using pre-defined terms. Unsolicited adverse events will be reported using a recognised medical term or diagnosis that accurately reflects the event.

Adverse events will be assessed by the Investigator, or a medically qualified study team member, for severity, relationship to study vaccine, action taken, outcome and whether the event meets criteria as an SAE according to the following guidelines:

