10.5 Adverse Events (AEs)

An adverse event is defined as any untoward medical occurrence in a participant administered a pharmaceutical product and does not necessarily have a causal relationship with this treatment.

All AEs entered on the eCRF will be coded according to the Medical Dictionary for Regulatory Activities (MedDRA) Version 23.0 or later.

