10.5.5.1 Handling of Solicited AE (eDiary) data

Solicited adverse events are recorded in the eDiary for 7 days post-vaccination (Day 0 to Day 7, Day 28 to Day 35, and Month 3 to Month 3 + 7 days [only applicable for booster participants]). All solicited AEs are considered causally related to the study treatment.

Solicited local symptoms including pain, induration (swelling), warmth, and erythema (redness), and solicited systemic symptoms including feverishness, chills, myalgia (muscle ache), fatigue (tiredness), headache, nausea, arthralgia (joint ache), and malaise (a general feeling of unwell) will be reported in a standardised manner over a period of 7 consecutive days after vaccination.

These solicited AEs and their intensity grades are based on the Food and Drug Administration (FDA) Guidance on Toxicity Grading Scale as described in Appendix 1 of the Protocol. If induration (swelling) or erythema (redness) are recorded as < 25mm in diameter in the eDiary, then this will be categorised as no event (grade 0) for the purpose of analysis. Derived intensity grades for induration and erythema are done based only on the numeric value of the parameter assessed, and clinical signs and symptoms will not be considered.

In addition, oral temperature will also be recorded for 7 days post-vaccination. Fever is defined as oral temperature $\geq 38^{\circ}\text{C}$ and the intensity grades are derived as specified in Appendix 1 of the Protocol.

Solicited AEs with missing intensity will not be included in the 'Any' count of the respective solicited AE.

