10.9.1 Unsolicited AE Missing or Partial Dates

Unsolicited AEs will be considered treatment-emergent unless the partial start date indicates that the event began prior to first vaccination, i.e. if the month and/or year are before the month of first study vaccination.

For the purpose of determining if the unsolicited AEs falls within 28 days of each vaccination (vaccination date + 27 days), the following imputation of missing and partial start dates will be performed:

Missing day, month, and year

The day, month, and year of date of first vaccination will be assigned to the missing fields.

Missing day and month

If the year of the incomplete start date is the same as the year of the date of first vaccination, then the day and month of the date of first vaccination will be assigned to the missing fields.

If the year of the incomplete start date is before the year of the date of first vaccination, then December 31 will be assigned to the missing fields.

If the year of the incomplete start date is after the year of the date of first vaccination, then 01 January will be assigned to the missing fields.

Missing month only

The day will be treated as missing and both month and day will be replaced according to the above procedure.

Missing day only

If the month and year of the incomplete start date are the same as the month and year of the date of first vaccination, then the day of the date of first vaccination will be assigned to the missing day.

If either the year is before the year of the date of first vaccination or if both years are the same but the month is before the month of the date of first vaccination, then the last day of the month will be assigned to the missing day.

If either the year is after the year of the date of first vaccination or if both years are the same but the month is after the month of the date of first vaccination, then the first day of the month will be assigned to the missing day.

If the stop date is complete and the imputed start date is after the stop date, then the start date will be imputed using the stop date.

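### No planned table reports the first primary endpoint as worded, and the SAP does not say whether solicited reactions count in the primary AE and Grade 3 or greater incidences

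*SAP*

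**What the plan says.** SAP 12.7.1 opens the primary endpoints with "Safety and reactogenicity of the vaccine(s): incidence of AEs, SAEs" and, at or above the stated grade, "Grade 3 study vaccine-related AEs within 4 weeks of vaccination".

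For the tables, SAP 12.7.1.1 says "The number and percentage of participants reporting each adverse event, including the number of events, will be summarised by SOC and PT coded" in MedDRA. It adds that "summaries will be provided for the subset of AEs, SAEs, and Grade 3 or greater AEs that occurred within 28 days of first vaccination", and likewise for the second vaccination. These subsets carry no filter for relatedness.

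SAP 12.7.2.1, under Other Safety Endpoints, lists Grade 3 or greater events in two ways: within 28 days of each vaccination whatever the cause, and related to study vaccines with no time limit.

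Solicited reactions follow a separate path. Protocol 8.2.4 says "Solicited adverse events are recorded in the eDiary up to 7 days post-vaccination. All other adverse events are recorded in the eCRF". SAP 10.5.5 pools the eDiary with the CRF reactogenicity page. SAP 12.7.2.2, also under Other Safety Endpoints, tabulates the result by symptom and by maximum severity, per vaccination and overall. On causality, SAP 10.5.5.1 says: "All solicited AEs are considered causally related to the study treatment".

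**The concern.** The endpoint names reactogenicity, and its third component has three conditions: Grade 3 or above, related to vaccine, within 4 weeks. A solicited systemic reaction such as Grade 3 chills on the day after vaccination meets the grade and timing conditions, and under SAP 10.5.5.1 it is also related. If the coded tables hold unsolicited events only, that participant has no event in the section labelled primary. The primary count could then be low, or zero, while a table under Other Safety Endpoints shows several severe reactions. With planned groups of about 9 to 16 participants, a few people change the headline percentage.

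A second risk comes from data entry. If some sites also enter solicited reactions as AEs and others do not, the coded tables will mix two definitions across sites, and possibly across groups.

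**Working it through.** **1. The plan's own safety figure.** SAP 8.1 and Protocol 10.1 state an 80% chance of seeing an event of 10% incidence in 16 participants. Check: 1 − 0.9^16 = 0.815, so it reproduces. The same formula gives 65.1% for 10 participants and 61.3% for 9, the sizes at which Groups 1 and 4 closed (SAP 8.1). This figure is not in dispute.

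**2. Endpoint against tables.**

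| Place | Events | Window | Related to vaccine only | Grade 3 or above |
|---|---|---|---|---|
| First primary endpoint, third component | AEs, under safety and reactogenicity | 4 weeks | yes | yes |
| SAP 12.7.1.1 subsets | coded AEs, scope not stated | 28 days | no | yes |
| SAP 12.7.2.1, 28-day rows | coded AEs, scope not stated | 28 days | no | yes |
| SAP 12.7.2.1, related rows | coded AEs, scope not stated | none | yes | yes |
| SAP 12.7.2.2 | solicited only | 7 days | all deemed related (10.5.5.1) | by symptom |

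No row below the first meets all its conditions. The 12.7.1.1 subsets fit the second primary endpoint (vaccines with nivolumab), which has no relatedness condition. No row combines solicited and unsolicited events.

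**3. Scope of the coded tables.** The SAP does not state it. The indications that they hold unsolicited events only are:
- the date rule in 10.9.1 opens "For the purpose of determining if the unsolicited AEs falls within 28 days of each vaccination";
- investigator causality in 10.5.2 is assigned to unsolicited AEs;
- the discontinuation rows in 12.7.2.1 draw on the unsolicited AE page of the eCRF;
- 10.5.5 pools solicited data only from the diary and the reactogenicity page, and describes no MedDRA coding for them.

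Against this, Protocol 8.2.4 also says that all adverse events are recorded in the eCRF, and SAP 10.5 codes whatever is entered there as an AE.

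**4. Direction and size on the unsolicited-only reading.** Let pu be the share of participants with an unsolicited event of a given class and ps the share with a solicited one. The combined share lies between max(pu, ps) and min(1, pu + ps); under independence it is 1 − (1 − pu)(1 − ps). A table of unsolicited events shows pu, which cannot exceed the combined share. The documents give neither rate, so the following values are assumed:

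| Class | pu (shown) | ps | Combined, independent | Bounds |
|---|---|---|---|---|
| Grade 3+ | 5% | 5% | 1 − 0.95×0.95 = 9.8% | 5–10% |
| Grade 3+ | 5% | 10% | 1 − 0.95×0.90 = 14.5% | 10–15% |
| Grade 3+ | 5% | 15% | 1 − 0.95×0.85 = 19.3% | 15–20% |
| Any grade | 40% | 50% | 1 − 0.60×0.50 = 70% | 50–90% |
| Any grade | 40% | 80% | 1 − 0.60×0.20 = 88% | 80–100% |

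The gap is zero if everyone with a solicited event also has a counted event of the same class, or if solicited events are also entered as AEs.

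**5. What it could look like in one group (assumed counts).** Three of 16 have a Grade 3 solicited reaction and nobody has an unsolicited one. An unsolicited-only row reads 0/16 (exact 95% CI 0 to 20.6%); a combined row reads 3/16 = 18.8% (4.0 to 45.6%).

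**The case against.** The strongest reply is that exclusion is never stated. Protocol 8.2.4 has all AEs in the eCRF, Protocol 8.2.6.1 includes solicited events among those whose resolution date goes on the eCRF, and the silence of Protocol 10.2.2.6.1 and SAP 6.1 fits equally well with no exclusion at all. This stands. A reader might infer that the plan drops solicited reactions and therefore understates its rates; the documents support only the conditional statement.

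Nor are the reactions hidden. Maximum severity is tabulated per vaccination and overall, with a sensitivity analysis and listings, and Tables 14.3.2.27.a, 14.3.2.27.b and 14.3.2.28 are marked for both the DMC and the interim analysis. This stands too: the gap is in the primary incidence, not in disclosure or monitoring.

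Two further inferences fail. SAP 12.7.1.1 cannot understate a vaccine-related rate, because it contains none. And three Grade 3 solicited reactions of any kind in the first 20 dosed do not by themselves meet the hold rule: Protocol 3.1.3 requires the same local or the same systemic event, so the example in step 5 need not trigger it.

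Finally, safety is descriptive and no test uses the combined row. That limits the consequence. It does not supply the missing estimate for a stated primary endpoint.

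**Conclusion.** The mismatch in step 2 holds on either reading of scope: no planned table gives vaccine-related events of Grade 3 or above within 4 weeks, and none combines the two streams under the endpoint that names reactogenicity.

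That the coded tables hold unsolicited events only is a strong inference, not a stated rule. If it is right, the primary any-AE and Grade 3 incidences are at most the combined ones. The difference cannot be sized from the documents and may be zero; the percentages in steps 4 and 5 are illustrations only. The point goes beyond labelling because the remedy can change the primary incidence that is reported. It should be fixed, but it does not put safety monitoring in doubt.

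**What to change.** In SAP 12.7.1.1, add two rows for each vaccination, with a 28-day window: participants with at least one AE, and participants with at least one vaccine-related AE of Grade 3 or above. Count solicited and unsolicited events together and each participant once. Name the denominator, since 12.7.2.2 uses participants with diary or reactogenicity data while the default in 12.0 is the population N. Keep the separate tables, label each as solicited, unsolicited or both, and name 12.7.2.2 as part of the primary reactogenicity endpoint.

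Two conflicts must be reconciled first:
- **Causality of solicited events.** SAP 10.5.5.1 relates all of them to study treatment, which in Groups 3 and 4 includes nivolumab. Protocol 8.2.4.2 makes only vaccination site reactions automatically related and leaves the rest to the investigator. The choice decides which systemic reactions enter the vaccine-related row; taking all of them could overstate it against the protocol.
- **Duplicate records.** SAP 10.5.5 takes the maximum grade from either source; 10.10 selects the CRF record for the primary analysis.

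The cost is a few derived rows from data already collected and graded, plus the work of settling these two rules. The headline AE rate may look less favourable.

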12.7.1.2 Laboratory Data

The number and percentage of participants with investigator assessed potentially clinically significant post-baseline values will be tabulated by laboratory category (haematology, biochemistry). Potentially clinically significant laboratory values as assessed by the investigator will be documented as AEs.

ALT and AST at each scheduled time point (Baseline, Day 7, Day 28, Day 35, Month 3, Month 6, and Month 9) and changes from baseline at each time point will be summarised by treatment group using descriptive statistics.

Haematology and biochemistry (including liver function tests) laboratory parameters listed in Table 6 will be presented using line plots of laboratory results by parameter and time point (including unscheduled visits) by participant.

Laboratory data values of the form of " $< x$ " (i.e., below the lower limit of quantification) or " $> x$ " (i.e., above the upper limit of quantification) will be imputed as " x " in the calculation of toxicity grading but displayed as " $< x$ " or " $> x$ " in the listings. Standard International (SI) units will be used for all laboratory parameters displayed in the figures and listings.

Table 6 Laboratory Tests

Category	Parameters
Haematology	leukocytes, basophils, basophils/leukocytes, eosinophils, eosinophils/leukocytes, lymphocytes, lymphocytes/leukocytes, monocytes, monocytes/leukocytes, neutrophils, neutrophils/leukocytes, haematocrit, haemoglobin, erythrocyte mean corpuscular haemoglobin, erythrocyte

Category	Parameters
	mean corpuscular haemoglobin concentration, erythrocyte mean corpuscular volume, erythrocytes, erythrocyte cell morphology, erythrocytes distribution width, platelets, fibrotest score, fibrotest stage, prothrombin intl. normalised ratio, prothrombin time, AST to platelet ratio index
Biochemistry (including liver function tests)	alanine aminotransferase, aspartate aminotransferase, gamma-glutamyl transpeptidase, alkaline phosphatase, bilirubin, direct bilirubin, urea nitrogen, creatinine, potassium, sodium, albumin, haptoglobin, alpha-2 macroglobulin, apolipoprotein A1
Urinalysis (dipstick)	specific gravity, pH, erythrocytes, protein, glucose, ketones, bilirubin, urobilinogen, leukocytes, nitrite
Urinalysis (drug screen)	amphetamine, barbiturates, benzodiazepine, cannabinoids, cocaine, methadone, opiate, phencyclidine, propoxyphene, tricyclic antidepressants
HBV disease markers	HBsAg, HBsAb, HBeAg, HBeAb, HBV DNA, HBcAb
Viral measurements	HIV antibodies, HCV antibodies, HDV antibodies

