#### ***7.4.2 Laboratory Safety Tests***

Laboratory safety tests will be performed at each of the timepoints according to [Table 2](#), as per [Sections 7.1.4.1](#) and [7.1.4.2](#). Extra laboratory safety tests may be performed if the Investigator deems them to be necessary to fully evaluate an adverse event. In the event that the Investigator elects to order non-protocol-specified laboratory tests, the Investigator must record the rationale for the tests and a determination of clinical significance of the result in the source documents. The Investigator must keep the local Medical Monitor informed of adverse events of clinical significance.

Abnormal results and findings will be discussed as applicable with the participant, and the participant will be referred for follow-up with their healthcare provider if necessary.

Results from the LFTs obtained on the study must be reviewed by the Investigator (or a designee who is a medically qualified study team member) and managed in accordance with the study centre procedures. The clinical significance of all results outside of the normal range will be determined by the Investigator and may be reported as an adverse event at the discretion of the Investigator.

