## **8.2 Adverse Events**

### ***8.2.1 Definitions***

#### ***8.2.1.1 Adverse Event***

An adverse event is:

- Any untoward medical occurrence in a participant or clinical investigation subject administered a pharmaceutical product and which does not necessarily have to have a causal relationship with this treatment

- An adverse event can therefore be any unfavourable and unintended sign (including an abnormal laboratory finding), symptom or disease temporally associated with the use of study vaccine, whether or not considered related to the investigational product

An adverse event includes but is not limited to:

- Any clinically significant worsening of a pre-existing condition
- An adverse event occurring from overdose (i.e. a dosage higher than that prescribed by a healthcare professional for clinical reasons, or a dosage higher than that described in the Investigator's Brochure or on the marketed product label) of an investigational or marketed product, whether accidental or intentional
- An adverse event occurring from abuse (e.g. use for non-clinical reasons) of an investigational or marketed product
- An event related to a medical procedure or associated with the discontinuation of the previous use of an investigational or marketed product required by protocol (protocol related adverse event)
- Not all vital sign or laboratory abnormalities will be considered an adverse event. Usually these will be considered as an adverse event:
  - If Grade 3 (severe) or greater in severity
  - If judged to be clinically significant by the Investigator
  - If accompanied by clinical symptoms
  - If meeting the definition of a SAE
  - If resulting in dose modification, interruption or discontinuation of study vaccine
  - If requiring specific treatment

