#### 10.2.2.6.2 Laboratory Safety Tests

Severity grading using the toxicity table in [Appendix 1](#) will be assigned to laboratory safety values where applicable. Laboratory results in reported units and standard international (SI) units will be listed, including high and low flags, severity grades where applicable, the corresponding normal range and clinical significance.

Laboratory safety tests summaries will be based on results in SI units. Absolute and change from baseline results, including the worst change for each variable for each participant will be summarised using descriptive statistics.

Treatment emergent out of range results with the corresponding severity grade, normal ranges, baseline results and clinical significance will be separately listed. Shift tables will be used to show changes from baseline at each timepoint and the worst change in each participant and scatterplots of the worst change will be produced. The number of participants showing shifts of at least two severity grades will be summarised.

The number of participants with treatment emergent clinically significant laboratory safety test results and laboratory safety test results of Grade 3 or 4 will be summarised.

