12.7.1.3 Vital Signs

Vital sign values will be considered potentially clinically significant if they meet either the low or high potentially clinically significant criteria listed in Table 7. The number and percentage of participants with any potentially clinically significant post-baseline value overall and by each criteria will be tabulated.

Table 7 Criteria for Potentially Clinically Significant Vital Signs

Vital Sign Parameter (unit)	Lower Limit	Upper Limit
Pulse rate (beats per minute)	< 45	> 130
Systolic blood pressure (mmHg)	< 80	> 155
Diastolic blood pressure (mmHg)		> 100
Temperature (°C)		≥ 39.0

A graphical display of each parameter by time point will be presented similarly to laboratory data.

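### Potentially clinically significant values, a primary endpoint, have numeric Grade 3 limits for vital signs but only open-label investigator judgement for laboratory tests; an objective laboratory count should be added

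*SAP*

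**What the plan says.** The endpoint is "Number and proportion of participants within each treatment group with potentially clinically significant laboratory values and vital signs within each treatment group" (SAP 12.7.1; same wording in protocol Section 2). The protocol does not define *potentially clinically significant*. The SAP does so in two ways.

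- **Vital signs (SAP 12.7.1.3).** Values count "if they meet either the low or high potentially clinically significant criteria listed in Table 7". The output is: "The number and percentage of participants with any potentially clinically significant post-baseline value overall and by each criteria will be tabulated".
- **Laboratory tests (SAP 12.7.1.2).** "The number and percentage of participants with investigator assessed potentially clinically significant post-baseline values will be tabulated by laboratory category", the categories being haematology and biochemistry. No numeric limit is given.

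Protocol 5.9 states that the study is open label and that the study team knows the treatment.

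Protocol 10.2.2.6.2 asks for a summary of "The number of participants with treatment emergent clinically significant laboratory safety test results and laboratory safety test results of Grade 3 or 4". SAP 12.7.2.3, under other safety endpoints, tabulates derived toxicity grades for each parameter and direction of change, at baseline and at the worst post-baseline result.

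On adverse events (AEs), SAP 12.7.1.2 says "Potentially clinically significant laboratory values as assessed by the investigator will be documented as AEs". Protocol 7.4.2 says that out-of-range results "may be reported as an adverse event at the discretion of the Investigator", and 7.1.4 closes the same way. Protocol 8.2.1.1 says that laboratory and vital-sign abnormalities are usually AEs under any of six criteria. One is "If Grade 3 (severe) or greater in severity"; the next is a judgement of clinical significance by the investigator.

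**The concern.** The two halves of one primary endpoint measure different things. The vital-sign half depends only on the reading. The laboratory half depends on whether an investigator who knows the allocation regards the value as significant. Immune-related toxicity is expected mainly in the groups given nivolumab, so the threshold for flagging could differ between groups even if the values do not.

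An objective count beside the judged one would let a reader see whether that had happened. The protocol asks for Grade 3 or 4 results as well as clinically significant ones. In the SAP, however, grades appear only parameter by parameter, outside the primary endpoint. The same judgement can also affect the Grade 3 or greater AE summaries, which are primary too, because the documents differ on when a laboratory value becomes an AE.

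**Working it through.** **1. The plan's own figure.** The documents give no figure for this endpoint. Their only design probability is an 80% chance that 16 participants show an event of 10% incidence (protocol 10.1, SAP 8.1). It reproduces: 1 − 0.9^16 = 0.815. Nothing here alters it.

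**2. Are the vital-sign limits Grade 3 limits?** The SAP does not say so; a comparison shows it.

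| Vital sign | SAP Table 7 | Start of Grade 3, protocol Appendix 1 |
|---|---|---|
| Pulse, low (beats/min) | < 45 | < 45 |
| Pulse, high (beats/min) | > 130 | > 130 |
| Systolic, low (mmHg) | < 80 | < 80 |
| Systolic, high (mmHg) | > 155 | > 155 |
| Diastolic, high (mmHg) | > 100 | > 100 |
| Temperature (°C) | ≥ 39.0 | 39.0 |

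Six of six agree. The vital-sign half is therefore a count of numeric values of Grade 3 or higher.

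**3. Can an equivalent laboratory count be read from SAP 12.7.2.3?** That section names 8 haematology and 11 biochemistry parameter-directions, 19 in all. For a group of N, the number of participants with Grade 3 or higher on any parameter lies between the largest single-row count and the smaller of N and the sum of the rows. As an illustration, suppose ALT and AST each show 4 of 16 and no other row has any. The any-parameter count is then between 4 (25%) and 4 + 4 = 8 (50%). The table cannot say which.

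**4. What do the DMC and interim packages contain?** SAP Section 16.0 lists Table 14.3.3.1.1 (PCS laboratory results) and two outputs on participants with out-of-range haematology or biochemistry results. It lists no toxicity-grade or shift table. The out-of-range outputs may show grades, but nothing says that they count them.

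**5. How much can judgement move the row?** The rates here are assumptions; the documents give none. Let 4 of 16 participants (25%) reach derived Grade 3 or higher.

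- 1 of the 4 flagged: 1/16 = 6.25%
- 2 of the 4 flagged: 2/16 = 12.5%
- 3 of the 4 flagged: 3/16 = 18.75%

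Two groups with the same 25% could thus read 6.25% and 18.75%. This ignores Grade 1 or 2 values that an investigator may also flag. One participant is worth 1/16 = 6.25 points in a group of 16, 1/10 = 10 points in Group 1 and 1/9 = 11.1 points in Group 4 (sizes of the closed groups from SAP 8.1).

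**6. Can SAP Appendix 1 supply the grades as it stands?** Not for every parameter.

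| Parameter (mEq/L) | Grade 3, both appendices | Grade 4, protocol Appendix 1 | Grade 4, SAP Appendix 1 |
|---|---|---|---|
| High sodium | 148–150 | > 150 | none |
| High potassium | 5.5–5.6 | > 5.6 | none |
| Low potassium | 3.1–3.2 | < 3.1 | none |
| Low sodium | 125–129 | < 125 | blank in the text available, possibly lost in extraction |

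A potassium of 6.5 or 2.8 is Grade 4 under the protocol table but falls outside every band of the SAP table. GGT and INR are in SAP Table 6 but have no grade in SAP Appendix 1.

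**7. The AE wording.** For a value judged significant, the SAP says *will* and protocol 8.2.1.1 says *usually*; these are close. For a Grade 3 or higher value not judged significant, 8.2.1.1 says *usually*, 7.1.4 and 7.4.2 say *may*, and the SAP sentence does not reach it. Protocol 3.1.4 also refers to Grade 3 laboratory AEs, so the passages must be reconciled.

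**The case against.** The defence has four good points.

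- A reader might infer that the SAP departed from the protocol without declaring it in SAP 6.1. The documents do not support that. Protocol 7.1.4 and 7.4.2 give the clinical significance of laboratory results to the investigator, and 10.2.2.6.2 assigns neither of its two counts to the primary endpoint.
- A reader might infer that Grade 3 or 4 values disappear from the report. They do not: 12.7.2.3 tabulates them for the graded parameters, out-of-range results are listed, and ALT and AST are summarised at every time point. Protocol 10.2.2.6.2 does not say whether its count is pooled or by parameter.
- A reader might see a flat contradiction on AEs. That is too strong. Protocol 8.2.1.1 also names investigator-judged significance, and 7.4.2 speaks of all out-of-range results, so discretion there can coexist with recording the significant ones.
- The safety analysis is descriptive, so no test depends on the row. The grading scale was written primarily for healthy volunteers, which is a reason to keep clinical judgement in patients with chronic hepatitis B.

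All four stand, and they support keeping the investigator row. They do not supply an any-parameter count, give the DMC or interim reader a graded table, or protect the laboratory half from knowledge of treatment.

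**Conclusion.** The laboratory half of this primary endpoint rests on open-label judgement alone, while the vital-sign half is a numeric Grade 3 or higher count. No laboratory count comparable to the vital-sign count is planned. The investigator-assessed count follows the protocol and is not an error. The direction and size of any bias are unknown; the percentages above illustrate what small groups allow and rest on assumed rates. Someone might also infer that Table 7 needs a condition on baseline. The documents show no error there, since the shift tables in SAP 12.7.2.4 already take account of baseline. No sample size or stated probability changes. This is a cheap improvement, not a defect that undermines the safety analysis.

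**What to change.** 1. In SAP 12.7.1.2 and Table 14.3.3.1.1, keep the investigator-assessed row. Add a row for participants with any post-baseline laboratory value of derived Grade 3 or higher whose baseline for that parameter was below Grade 3, overall and by laboratory category. That table is already in the DMC and interim list, so the new row reaches both.
2. Before deriving it, reconcile SAP Appendix 1 with protocol Appendix 1 on the Grade 4 limits for sodium and potassium, so that values beyond the Grade 3 band are counted.
3. State that parameters without a grade, such as GGT and INR, are covered by the investigator row only.
4. Reconcile SAP 12.7.1.2 with protocol 7.1.4, 7.4.2 and 8.2.1.1 on when a laboratory value is recorded as an AE, including a Grade 3 or higher value not judged significant.

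The cost is SAP wording and one extra row, mostly from grades already derived for 12.7.2.3. The drawback is that the reported laboratory rate may be higher.
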